At this visit, target and nontarget lesions identified at baseline by modified RECIST 1.1 will be assessed as usual.

New lesions will be classified as measurable or nonmeasurable, using the same size thresholds and rules as for baseline lesion assessment in RECIST 1.1. From measurable new lesions, up to 5 lesions total (up to 2 per organ), may be selected as New Lesions – Target. The sum of diameters of these lesions will be calculated, and kept distinct from the sum of diameters for target lesions at baseline. All other new lesions will be followed qualitatively as New Lesions – Non-target.

Assessment at the Confirmatory Imaging

On the confirmatory imaging, the participant will be classified as progression confirmed (with an overall response of iCPD), or as showing persistent unconfirmed progression (with an overall response of iUPD), or as showing disease stability or response (iSD/iPR/iCR).

Confirmation of Progression

Progression is considered confirmed, and the overall response will be iCPD, if ANY of the following occurs:

- Any of the factors that were the basis for the iUPD at the previous visit show worsening
  - For target lesions, worsening is a further increase in the sum of diameters of
  - ≥5 mm, compared to any prior iUPD time point
  - For nontarget lesions, worsening is any significant growth in lesions overall, compared to a prior iUPD time point; this does not have to meet the "unequivocal" standard of RECIST 1.1
  - For new lesions, worsening is any of these:
    - An increase in the new lesion sum of diameters by ≥5 mm from a prior iUPD time point
    - Visible growth of new nontarget lesions
    - The appearance of additional new lesions
- Any new factor appears that would have triggered PD by modified RECIST 1.1

Persistent iUPD

Progression is considered not confirmed, and the overall response remains iUPD, if:

Eisai Confidential Page 120 of 138

- None of the progression-confirming factors identified above occurs AND
- The target lesion sum of diameters (initial target lesions) remains above the initial PD threshold (by modified RECIST 1.1)

Additional imaging for confirmation should be scheduled 4 to 8 weeks from the imaging on which the initial iUPD is seen. This may correspond to the next visit in the original visit schedule. The assessment of the subsequent confirmation imaging proceeds in an identical manner, with possible outcomes of iCPD, iUPD, and iSD/iPR/iCR.

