### Appendix Table 2: Imaging and Treatment After First Radiologic Evidence of Progressive Disease

	Clinically Stable		Clinically Unstable	
	Imaging	Treatment	Imaging	Treatment
First radiologic evidence of PD by modified RECIST 1.1	Repeat imaging at 4 to 8 weeks to confirm PD.	May continue study treatment	Repeat imaging at 4 to 8 weeks to confirm PD per investigator's discretion only.	Discontinue treatment.
Repeat tumor imaging confirms PD (iCPD) by iRECIST per investigator assessment	No additional imaging required.	Discontinue treatment.	No additional imaging required.	Not applicable
Repeat tumor imaging shows iUPD by iRECIST per investigator assessment	Repeat imaging at 4 to 8 weeks to confirm PD. May occur at next regularly scheduled imaging visit.	Continue study treatment at the investigator's discretion.	Repeat imaging at 4 to 8 weeks to confirm PD per Investigator's discretion only.	Discontinue treatment.
Repeat tumor imaging shows iSD, iPR, or iCR by iRECIST per investigator assessment.	Continue regularly scheduled imaging assessments.	Continue study treatment at the investigator's discretion.	Continue regularly scheduled imaging assessments.	May restart study treatment if condition has improved and/or clinically stable per investigator's discretion. Next tumor imaging should occur according to the regular imaging schedule.

iCPD = confirmed progressive disease per iRECIST, iCR = complete response per iRECIST, iRECIST = modified Response Evaluation Criteria in Solid Tumors 1.1 for immune-based therapeutics, iSD = stable disease per iRECIST, iUPD = unconfirmed progressive disease per iRECIST, PD = progressive disease, RECIST 1.1 = Response Evaluation Criteria in Solid Tumors 1.1.

Eisai Confidential Page 123 of 138

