point assignment	between IR and PD), the IR assessment should subsequently be corrected to PD for reporting purposes to the date of the prior			
	designation of IR. We recognize that these lesions may remain stable during the time of observation, but, even if this is the			
	case, the initial designation of IR should be changed to PD.			

a FDG = fluorodeoxyglucose, IR = Indeterminate Response, LYRIC = LYmphoma Response to Immunomodulatory Therapy Criteria, PD = progressive disease, PPD = product of perpendicular diameters, SPD = sum of product diameters, TL = target lesion.

Source: Cheson, et al. 2016.

Eisai Confidential Page 130 of 138

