5.4.2.4 Progression-free Survival

In PFS analysis Subjects without disease progression or death will be censored at the time of the last tumor assessment. Subjects who started new anticancer therapies without documented progression of disease will be censored at the last adequate tumor assessment on or prior to the start of new anticancer therapies. Determination of the date of PFS event or censoring is summarized in [Table 3](#) below.

Table 3 PFS Event and Censoring Rules

No.	Situation	Date of Progression or Censoring	Outcome
1	No baseline or postbaseline adequate tumor assessments	Date of first dose	Censored
2	Progression documented between scheduled visits, on or prior to new anticancer therapy	Date of first qualified*** PD assessment	PFS Event
3	No progression at the time of data cutoff	Date of last adequate assessment on or prior to data cutoff	Censored
4	New anticancer therapy started	Date of last adequate assessment on or prior to the start of new anticancer therapy	Censored
5	Death before first PD assessment, on or prior to start of new anticancer therapy	Date of death	PFS Event
6	Death between adequate assessment*	Date of death	PFS Event
7	Death or progression after more than one missed visit/tumor assessment**	Date of last adequate assessment before missed tumor assessments	Censored

CR = complete response, ic = iRECIST-confirmed, iu = iRECIST-unconfirmed, PD = progressive disease, PR = partial response, SD = stable disease.

Note:

* Adequate tumor assessment is radiologic assessment of CR, PR, SD, non-CR/non-PD or PD as determined by investigators at regular interval as defined in the protocol. Any tumor assessments after new anticancer therapy will not be considered in the definition of PFS.

** More than one missed visit/adequate tumor assessment is defined as:

- having the duration between two consecutive tumor assessments or the duration between the last adequate tumor assessment and death/PD being longer than (>) 97 days (for solid tumors because the scans are scheduled every 6 weeks \pm 7 days for this study).

*** Qualified PD is defined as:

- For modified RECIST: the documented PD per modified RECIST CRF page;
- For iRECIST: in the order of 1) the documented iCPD per iRECIST CRF page, or 2) the iUPD that has not be reset by subsequent iCR/iPR/iSD

NOTE: iCPD has to be within 8 weeks of iUPD, but not earlier than 4 weeks (i.e. \geq 28 days) of iUPD.

1. If the subject had PD or death, the following sequence will be applied:

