- If a subject did not have baseline or postbaseline adequate tumor assessments (No. 1), the subject will be censored at the date of the first dose. However, if the subject died within 35 days after the first dose date and did not receive any new anticancer therapy, it will be counted as a PFS event at the date of death.
- If subject has baseline tumor assessment but does not have any postbaseline adequate tumor assessments, the subject will be censored at the date of the first dose. However, if the subject died

within 97 days after the first dose date and did not receive any new anticancer therapy, it will be counted as a PFS event at the date of death.
 
 • If a subject has a baseline and at least one post-baseline adequate tumor assessment and had new anticancer therapy before PD or death (No. 4), the subject will be censored at the date of the last adequate tumor assessment on or prior to the date of new anticancer therapy • If a subject missed two or more tumor assessments (No. 7), the subject will be censored at the date of the last adequate tumor assessment before the occurrence of more than one missing assessment. Note that if a subject is censored by both of this criterion and start of new anticancer therapy criterion, the earliest censoring date will be used. • Otherwise, if a subject had PFS event (No. 2, No. 5 or No. 6), the earliest event date will be used. 
2. If a subject did not have PD or death, the censoring date will be the earliest censoring date if the subject met multiple censoring criteria (No. 1, No. 3, No. 4, No. 7).

PFS will be presented in subject data listings.

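### SAP Table 3 does not say which scan dates an iRECIST progression that has both iUPD and iCPD; read as precedence, confirmed progressions are dated 28 to 56 days later than unconfirmed ones

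*SAP*

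**What the plan says.** Row 2 of SAP Table 3 (5.4.2.4) gives the event date as "Date of first qualified* PD assessment". For iRECIST, the footnote says a PD qualifies "in the order of 1) the documented iCPD per iRECIST CRF page, or 2) the iUPD that has not be reset by subsequent iCR/iPR/iSD", and adds "NOTE: iCPD has to be within 8 weeks of iUPD, but not earlier than 4 weeks". The PFS and DOR definitions in SAP 5.1.1 and 5.1.2 also use the first documentation of qualified progression and refer to 5.4.2.4. SAP 5.4.2.2 carries DOR over to Dose Escalation.

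The protocol's definitions (9.7.1.1.1 and 9.7.1.1.2) instead end PFS and DOR at the first documentation of *confirmed* progression. Under Protocol Appendix 2, the first visit with modified RECIST 1.1 progression is always iUPD, and iUPD may persist over several scans before it is confirmed or reset. Appendix 2 has no dating rule for a confirmed progression. The lymphoma criteria do have one: under LYRIC, when true progression follows an indeterminate response (IR) with no objective response between, "the IR assessment should subsequently be corrected to PD for reporting purposes to the date of the prior" designation.

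**The concern.** An iUPD that is later confirmed was never reset. It therefore meets item 2 of the footnote and comes before the iCPD, so the word first points to the iUPD date. The ranking points to the iCPD date.

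If the ranking is applied, two subjects with the same first progression scan get different event dates according to whether that progression was later confirmed. Whether a confirmatory scan is done is not purely a matter of disease. Protocol 9.5.1.3.1 asks for confirmation in clinically stable subjects. For clinically unstable subjects, Appendix Table 2 says "Repeat imaging at 4 to 8 weeks to confirm PD per investigator's discretion only". Scans that continue after treatment stops without confirmed progression (9.5.1.3.1) reduce this contrast but do not remove it.

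The reading of the results is at stake. Under iCPD dating, iRECIST PFS exceeds modified RECIST PFS by about one scan interval in every subject confirmed at the first repeat scan, as well as wherever a progression was reset. A reader could mistake the first effect for pseudo-progression.

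**Working it through.** **Inputs**
- iUPD-to-iCPD window: 4 to 8 weeks (SAP Table 3 note).
- Solid-tumor scans: every 6 weeks, ±7 days (SAP Table 3 note; Protocol 9.5.1.3.1).
- Illustration: first iUPD at the Week 6 scan, Day 42.

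**The plan's window in days.** 4 × 7 = 28 and 8 × 7 = 56. The scan schedule gives the same range: consecutive scans 42 days apart, each ±7 days, lie 42 − 14 = 28 to 42 + 14 = 56 days apart.

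**Confirmed at the first repeat scan**
- Ranking applied: 42 + 28 = Day 70 to 42 + 56 = Day 98, nominally 42 + 42 = Day 84.
- The same progression never confirmed (item 2): Day 42.
- Difference: 28 to 56 days, nominally 42.
- If first qualified governs: Day 42 in both cases, difference 0.

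**One persistent iUPD, then iCPD at the second repeat scan**
- Each repeat scan anywhere in its own window: 2 × 28 = 56 to 2 × 56 = 112 days after the first iUPD, nominally 2 × 42 = 84.
- All scans at scheduled Weeks 6, 12 and 18: (126 − 7) − (42 + 7) = 70 to (126 + 7) − (42 − 7) = 98 days, nominally 84.

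**Which iUPD starts the 8-week limit.** Take iUPD on Day 42, persistent iUPD on Day 84 and iCPD on Day 126, with the ranking applied.
- Counted from the latest iUPD: 126 − 84 = 42 days, inside 28 to 56. The iCPD qualifies and the event is Day 126.
- Counted from the first iUPD: 126 − 42 = 84 days, more than 56. The iCPD does not qualify and the event reverts to the un-reset iUPD on Day 42.
- Two 28-day gaps put the iCPD exactly 56 days after the first iUPD. It then qualifies on either count, so counting from the first iUPD does not always give a zero shift.

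The protocol does not settle the starting point. For persistent iUPD, Appendix 2 says "Additional imaging for confirmation should be scheduled 4 to 8 weeks from the imaging on which the initial iUPD is seen". For clinically stable subjects in the same situation, Appendix Table 2 says "Repeat imaging at 4 to 8 weeks to confirm PD. May occur at next regularly scheduled imaging visit".

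**The case against.** The strongest reply is that the footnote is already usable: take the iCPD if one is documented, otherwise the un-reset iUPD. The words about order have little purpose unless they set precedence, and this reading agrees with the protocol's confirmed progression. That stands, and precedence is the more natural reading. It does not remove the concern, because it is the reading under which confirmed and unconfirmed progressors are dated by different rules.

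A second reply is that iUPD dating makes iRECIST PFS largely repeat modified RECIST PFS, since the first modified RECIST progression is the iUPD. This is a real cost. But the two would then differ mainly where an iUPD was reset, which is the feature iRECIST adds.

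A third reply is that the derivation specifications (SAP 9), which are not among these documents, may fix the date. They may, but the SAP's own definition should give it.

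Four stronger readings might be inferred and are not supported:
- *The SAP already settles on iUPD.* The sequence under Table 3 says "Otherwise, if a subject had PFS event (No. 2, No. 5 or No. 6), the earliest event date will be used". That chooses among rows 2, 5 and 6; it does not define the row 2 date.
- *Appendix 2 and Appendix Table 2 contradict each other.* Appendix 2 goes on to allow the next scheduled visit too. Only the starting point of the SAP's limit is open.
- *An average shift can be stated.* The documents give no fraction confirmed, and the planned summaries are Kaplan-Meier medians and quartiles and subject listings, not means.
- *The SAP conceals a changed endpoint.* Qualified PD is openly defined and cross-referenced, and Protocol 9.7.1 leaves further analytical detail to the SAP. Not listing it in SAP Section 7 is a housekeeping matter.

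**Conclusion.** The point holds as a minor one. Read as precedence, Table 3 dates a progression confirmed at the first repeat scan 28 to 56 days later (nominally 42) than the same progression left unconfirmed. After one persistent iUPD, the iCPD is 56 to 112 days after the first iUPD (70 to 98 if all scans are at scheduled Weeks 6, 12 and 18), and whether that date is used depends on which iUPD starts the 8-week limit. Read by the word first, there is no shift at all. These sizes assume 6-weekly scans and repeat scans within the 4 to 8 week window.

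The scope is narrow: descriptive iRECIST PFS and DOR in Dose Escalation. Modified RECIST results, ORR, DCR and OS are unaffected. Dose Expansion will not be analysed (SAP 3.2.2), and no statistical comparisons are planned (SAP 5.3.3). A reader might infer that a study conclusion is at risk; the documents do not support that.

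**What to change.** Add to the qualified-PD note: *For iRECIST PFS and DOR the event date is the first iUPD not later reset by iSD/iPR/iCR, whether or not iCPD follows.* This dates confirmed and unconfirmed progressors alike, matches the protocol's LYRIC back-dating, and makes the starting point of the 8-week limit irrelevant to the event date.

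The cost is one sentence and at most a small change to derivation code. There are three downsides. iRECIST times will be shorter than under iCPD dating. iRECIST PFS will differ from modified RECIST PFS mainly where an iUPD was reset. The rule also departs from a literal reading of the protocol's confirmed progression, which a line in SAP Section 7 could optionally record. If the sponsor prefers iCPD dating, the note should say so and name the iUPD from which the 4 to 8 weeks run.

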5.4.2.5 Overall Survival

OS is defined as the time from the date of first dose to the date of death from any cause. Subjects who are lost to follow up or withdrew consent will be censored at the date subject was last known to be alive, or the cutoff date, whichever occurs first. Subjects who remained alive will be censored at the time of data cutoff. Determination of the date of OS event or censoring is summarized in Table 4 below.

Table 4 OS Event and Censoring Rules

Situation	Date of Event or Censoring	Outcome
Death no later than data cut-off date	Date of death	OS Event
Death after data cut-off	Date of data cut-off	Censored
Subject still alive at data cut-off	Date of data cut-off	Censored
Subject lost to follow-up or withdrawal of consent before data cut-off	Date of last known to be alive	Censored
Note: date of subject disposition may be used as last known alive date if the disposition reason is Subject Choice, Withdrawal consent and Treatment ongoing at data cut-off.		

OS will be presented in subject data listings.

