### 9.1.3.4 Follow-Up Phase

The Follow-Up Phase will begin immediately after the off-treatment assessments have been completed and will continue for up to 2 years or until study subject is deceased, or until the completion of the primary analysis, whichever is earlier, unless the subject withdraws consent or until the sponsor terminates the study.

Subjects who discontinue study treatment before disease progression will continue to undergo disease assessment every 6 weeks in case of solid tumors and 12 weeks in case of lymphomas until documentation of disease progression or start of another anticancer therapy.

Subjects will be followed every 12 weeks ( $\pm 1$  week) for survival, performance status and subsequent anticancer treatments. The sponsor may decide to terminate survival follow-up anytime during the Extension Phase or when all subjects have discontinued study treatment. Survival follow-up will be conducted in person or via phone call.

In the Follow-Up Phase, subjects will be treated by the investigator according to the prevailing local standard of care.

Eisai Confidential Page 58 of 138

[figure not shown]
The sponsor may decide to terminate survival follow-up anytime during the Extension Phase or when all subjects have discontinued study treatment.

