## 9.3.3 Removal of Subjects from Therapy or Assessment

The investigator may withdraw the subject from the study at any time for safety or administrative reasons. The subject may stop study drug or withdraw from the study at any time for any reason.

The investigator may discontinue treating a subject with study treatment or withdraw the subject from the study at any time for safety or administrative reasons. The subject may decide to discontinue study treatment or withdraw from the study at any time for any reason. The reason for discontinuation will be documented. If a subject discontinues study treatment, the subject will enter the Follow-Up Period and complete protocol-specified off-treatment visits, procedures, and survival follow-up unless the subject withdraws consent. The investigator should confirm whether a subject will withdraw from study treatment but agree to continue protocol-specified, off-treatment study visits, procedures, and survival follow-up, or whether the subject will withdraw consent. If a subject withdraws consent, the date will be documented in the source documents.

During the Follow-Up Period, subjects who have discontinued study treatment without progression should have disease assessments every 6 weeks in case of solid tumors and 12 weeks in case of lymphomas from the date of the last assessment until disease progression is documented or another anticancer therapy is initiated.

All subjects will be followed for survival every 12 weeks for up to 2 years, except where a subject withdraws consent or the sponsors choose to halt survival follow-up after completion of the primary study analysis.

[figure not shown]

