	Visit	1	2	3	3 3 4 5 5 5					6	7	8, 9, etc	98	100
	Day	-28 to -1	-3 to -1	1	1 2 8 14 15 16					1	15	1		
CRF	Procedures/Assessments								·					

or ruler). The lesion measurement is recommended to be based on the long axis diameter of the lesion, but measurement should be consistent throughout the study.

Eisai Confidential Page 94 of 138

z. Subjects who discontinue study will be followed for survival (in person visit or phone call is acceptable). Survival follow-up will be conducted on all subjects approximately every 12 weeks (±1 week), unless they withdraw consent.

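### The OS rule censors surviving subjects at the data cutoff without requiring evidence that they were alive on that date, so time after the last contact can be counted as survival

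*SAP*

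**What the plan says.** SAP 5.4.2.5 and its Table 4 sort subjects as follows.

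- A death on or before the cutoff is an event.
- "Death after data cut-off" is censored at the cutoff.
- "Subject still alive at data cut-off" is censored at the cutoff. The text above the table repeats this: "Subjects who remained alive will be censored at the time of data cutoff". Protocol 9.7.1.6.2 has the same sentence.
- "Subjects who are lost to follow up or withdrew consent will be censored at the date subject was last known to be alive". The cutoff replaces that date if it comes first.

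A note to Table 4 adds: "date of subject disposition may be used as last known alive date if the disposition reason is Subject Choice, Withdrawal consent and Treatment ongoing". The last of these reasons covers subjects whose treatment is still under way when the cutoff falls. Neither document says how being alive at the cutoff is established, and neither requires a status check at that date.

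On follow-up, Protocol Table 7 (footnote z) says "Survival follow-up will be conducted on all subjects approximately every 12 weeks", with a window of one week either way. Protocol 9.3.3 says "All subjects will be followed for survival every 12 weeks for up to 2 years". Protocol 9.1.3.4 adds: "The sponsor may decide to terminate survival follow-up anytime during the Extension Phase or when all subjects have discontinued study treatment".

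**The concern.** Table 4 has no row for a subject with no recorded death who is neither lost nor withdrawn and whose last contact came before the cutoff. Two kinds of subject fit that description: those between two 12-weekly contacts, and those whose survival follow-up the sponsor ended. Protocol 9.5.5 lists termination of the study by the sponsor as a discontinuation reason separate from loss to follow-up and withdrawal of consent, and the Table 4 note does not mention it. A programmer following the table would put both kinds in the row for living subjects.

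Deaths after the last contact would then go unseen while the subject stayed in the risk set to the cutoff, which raises the Kaplan-Meier curve. In a single-arm study no comparator offsets this. The PFS rule (SAP 5.4.2.4, Table 3) handles the parallel case differently: a subject without progression at cutoff is censored at the last adequate assessment, not at the cutoff itself.

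**Working it through.** **No figure to reproduce.** Neither document states an OS median, rate or event count. The check compares the two censoring rules by simulation, with 200,000 simulated subjects per scenario.

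**Inputs from the documents.** Contacts are every 12 weeks (Protocol 9.1.3.4 and Table 7). The cutoff comes 6 months after the last subject starts treatment (SAP 5).

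**Assumptions.** OS is exponential with true median M of 6, 9, 12 or 18 months. Accrual is uniform over 24 months. Status is learned only at 12-weekly contacts unless stated otherwise. The 2-year cap is not modelled.

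**Set-up.**

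- Death time T is exponential with rate ln 2 / M.
- Time from first dose to cutoff is C = 6 + Uniform(0, 24) months.
- Contact spacing is 84 / 30.4375 = 2.76 months, with a random start. L is the last contact.
- A death is known if T ≤ L or, with prompt reporting, if T falls before follow-up ends.
- Cutoff rule: time is T if known dead, otherwise C.
- Last-known-alive rule: time is T if known dead, otherwise L.

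**Check on the credited time.** The expected unobserved gap is half a contact interval, 2.76 / 2 = 1.38 months. The simulation gave 1.40 to 1.45 per subject not known dead. If follow-up stops 3 months before cutoff the expected gap is 3 + 1.38 = 4.38 (simulated 4.40 to 4.45). If it stops 6 months before, it is 6 + 1.38 = 7.38 (simulated 7.31 to 7.32).

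**Estimated median (months) under the cutoff rule:**

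| How status is learned | M = 6 | M = 9 | M = 12 | M = 18 | Error in 12-month OS (points) |
|---|---|---|---|---|---|
| Status check at cutoff | 6.01 | 9.02 | 12.06 | 18.03 | 0 to +0.2 |
| Deaths reported promptly | 6.00 | 8.99 | 11.98 | 18.01 | −0.1 to 0 |
| 12-week gap only | 6.03 | 9.24 | 12.53 | 19.16 | +1.0 to +1.4 |
| Follow-up stops 3 months early | 6.64 | 10.53 | 14.59 | not reached | +4.6 to +6.8 |
| Follow-up stops 6 months early | 8.40 | 13.57 | not reached | not reached | +9.2 to +15.3 |

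For the 12-week gap alone, the relative error in the median runs from (6.03 − 6) / 6 = +0.5% to (19.16 − 18) / 18 = +6.4%. Twelve-month OS is shown only for scale; neither document plans it.

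**Estimated median under the last-known-alive rule:**

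| How status is learned | M = 6 | M = 9 | M = 12 | M = 18 |
|---|---|---|---|---|
| Status check at cutoff | 6.01 | 9.02 | 12.06 | 18.03 |
| 12-week gap only | 5.97 | 8.98 | 12.00 | 17.95 |
| Follow-up stops 3 months early | 6.00 | 9.01 | 11.99 | 18.14 |
| Follow-up stops 6 months early | 6.01 | 8.98 | 11.97 | 18.11 |
| Deaths reported promptly, survivors seen every 12 weeks | 5.96 | 8.77 | 11.56 | 17.04 |

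The last row shows that this rule can err downward, by up to (17.04 − 18) / 18 = −5.3%.

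**Scale against sampling error.** With exponential OS and no censoring, the standard error of the median is about M / (√n × ln 2). At the 35 subjects anticipated for escalation (SAP 4) that is M / (5.916 × 0.693) = 0.24 M, or 24% of the median. A smaller number treated would make it larger.

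**The case against.** The best defence is that the SAP does not say what a reader might infer, namely that everyone not recorded as dead, lost or withdrawn is presumed alive. It speaks of subjects who are alive. The row for deaths after cutoff presupposes some status information dated later than the cutoff, and the Table 4 note shows that actual dates are used for some subjects. This stands: the documents do not state a presumption of survival. But no other row fits the subjects in question, so the presumption is what the table yields in practice.

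Contact is also often closer than every 12 weeks. Subjects on maintenance treatment are dosed every 3 weeks. Those with solid tumors who stop before progression are scanned every 6 weeks. Deaths reportable as serious adverse events up to 90 days after the last dose, or to the start of new anticancer therapy if earlier, must be notified within a day or so (Protocol 9.5.4.1). This also stands and narrows the gap. Later deaths still depend on the 12-weekly contacts.

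A reader might further infer from the early end of escalation and the decision to enrol no expansion subjects (SAP 3.2.2 and 7) that survival follow-up was cut short, so that the large errors apply. The documents do not say so. Protocol 9.3.3 speaks of halting survival follow-up after the primary analysis is complete, which would fall after the cutoff. Protocol 9.1.3.4 permits an earlier stop but none is planned.

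Nor does the 2-year cap explain errors of this kind. It runs from the end of the off-treatment assessments, so time credited beyond it can affect the curve only past 24 months.

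**Conclusion.** The gap is real: the plan allows censoring at the cutoff without documented survival at that date, and it gives no correct place to subjects whose contact ended earlier for administrative reasons. A general claim that OS is biased upward is not supported. The direction and size depend on how vital status is gathered, which the documents leave open. On the assumptions above, the upward error is negligible with a status check or prompt death capture, small with the contact gap alone, and substantial only with an early stop of follow-up that nobody has planned.

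Severity is low. OS is secondary, no statistical comparisons are made (SAP 5.3.3), and in the contact-gap case the error is well below sampling error. It is still worth correcting before the abbreviated report. OS is not among the analyses removed in SAP 7, Protocol 9.7.1.6.2 plans Kaplan-Meier medians and quartiles, and the individual times in the OS listing would carry the same unobserved follow-up.

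**What to change.** In SAP Table 4, replace the row for living subjects with two:

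1. Documented alive on or after the cutoff: censor at the cutoff.
2. No recorded death and not documented alive on or after the cutoff, for any reason including follow-up ended by the sponsor: censor at the last date known alive (last contact, visit, dose or scan).

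Align the sentence in SAP 5.4.2.5, and record in SAP 7 that it refines Protocol 9.7.1.6.2. Where possible, use a survival contact on or just after the cutoff as the status check. With that in place the two rules agree, and the slight downward bias of last-known-alive censoring (deaths captured faster than survivors are contacted) does not arise.

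The cost is one table row split in two and one derivation. The dates are already collected, and subjects documented alive at or after the cutoff are unaffected. The downside is a slightly shorter reported follow-up.
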